### **6.1.2 To decrease morbidity**

- i.e. the rate of reactivation and permanent consequences by prolonging the continuation treatment to one year.

### **6.1.3 To assess acute and late treatment toxicity**

## **6.2 GROUP 2: MULTISYSTEM “LOW RISK” PATIENTS**

### **6.2.1 To decrease morbidity**

- by reducing the rate of reactivation and permanent consequences. The value of prolonged continuation therapy for responders to initial treatment and the efficacy of 6 versus 12 months continuation treatment will be tested in a randomized way.

### **6.2.2 To increase the response rate**

- by applying a second course of initial treatment course according to arm A of the “RISK” group in patients with an insufficient response (intermediate and worse) to initial treatment at week 6.

### **6.2.3 To assess acute and late treatment toxicity**

## **6.3 GROUP 3: SINGLE SYSTEM MULTIFOCAL BONE AND LOCALIZED “SPECIAL SITES”**

### **6.3.1 To reduce morbidity**

i.e. the rate of reactivation and permanent consequences (as compared to the historical control group of the DAL HX 83/90 and LCH I and II studies).

## **7 STUDY DESIGN**

LCH III is an international, multicentric, prospective clinical study comprising

- a randomized clinical trial for multisystem “RISK” patients and

- a randomized clinical trial for multisystem “LOW RISK” patients and
- a pilot study for patients with single system MFB and localized “SPECIAL SITES”

## **8 REGISTRATION AND RANDOMIZATION**

### **8.1 REGISTRATION**

After confirmation of the diagnosis of a new patient, the registration form and the diagnostic evaluation forms have to be sent to the study subcenter or study reference center by fax or e-mail without delay together with the completed and signed consent form.

### **8.2 RANDOMISATION**

#### **8.2.1 Eligibility for randomization group 1 “RISK” patients**

- eligibility for the study
- multisystem disease with involvement of “RISK” organs

#### **8.2.2 Eligibility for randomization 2 “LOW RISK” patients**

- eligibility for the study
- multisystem disease without involvement of “RISK” organs
- response to initial therapy, i.e. regression (AD better) or resolution (NAD) after 6 weeks of initial treatment course 1

Randomisation will be performed by the study subcenter or study reference center promptly after the reception of the registration, diagnostic evaluation or follow up and consent forms. The information on the assigned treatment arm and the randomisation number will be forwarded to the participant by e-mail or fax without delay.

## **9 TREATMENT**

### **9.1 GROUP 1: MULTISYSTEM “RISK” PATIENTS**

consists of an initial treatment of one or two 6 week courses (according to

response) and a continuation treatment. The overall therapy duration is 12 months.

### **9.1.1 Treatment arm A**

#### **9.1.1.1 Initial treatment course 1**

Continuous oral prednisone (PDN) 40mg/m^2 daily in 3 doses as a 4-week course, tapering over a period of 2 weeks.

Vinblastine (VBL) 6 mg/m^2 i.v. bolus, day 1 of week 1, 2, 3, 4, 5, 6.

#### **9.1.1.2 Initial treatment course 2**

(starting without delay after course 1 for patients who are AD better or intermediate after course 1. Patients who are NAD after course 1 proceed to continuation treatment.).

Oral prednisone (PDN) 40mg/m^2 in 3 divided doses for 3 days every week, from week 7-12.

Vinblastine (VBL) 6 mg/m^2 i.v. bolus, day 1 of week 7, 8, 9, 10, 11, 12.

#### **9.1.1.3 Continuation treatment**

(starting after initial treatment at day 1 of week 7 in pts who are NAD after course 1 of initial treatment, or at day 1 of week 13 in pts who are NAD or AD-better after course 2 of initial treatment.

Continuous oral 6-mercaptopurine (6-MP) 50mg/m^2 daily until the end of month 12 from therapy start.

Pulses of oral prednisone PDN 40mg/m^2 in 3 doses, day 1-5 q 3 weeks, starting at day 1 of week 7 in patients NAD after course 1 or at day 1 of week 13 in patients NAD or AD better after course 2 until the end of month 12.

Vinblastine (VBL) 6mg/m^2 i.v. bolus, day 1 q 3 weeks, starting at day 1 of week 7 in patients NAD after course 1 or at day 1 of week 13 in patients NAD or AD better after course 2 until the end of month 12.

## **9.1.2 Treatment arm B**

### **9.1.2.1 Initial treatment course 1**

Continuous oral prednisone (PDN) 40mg/m^2 daily in 3 divided doses as a 4-week course, tapering over a period of 2 weeks.

Vinblastine (VBL) 6 mg/m^2 i.v. bolus, day 1 of week 1, 2, 3, 4, 5, 6 given before the MTX infusion.

Methotrexate 500 mg/m^2 24 hours-infusion with folinic acid (leucovorin) rescue, day 1 of week 1, 3, 5. 1/10 of the dose as i.v. bolus over 30 min, followed by 9/10 of the dose as 23.5 hours infusion with 2000ml/m^2 hydration.

Folinic acid 12mg/m^2 orally is given 24 hours and 30 hours after the stop of the MTX infusion (id est: 48 and 54 hours after start of MTX therapy).

### **9.1.2.2 Initial treatment course 2**

(starting without delay after course 1 for patients who are AD better or intermediate after course 1. Patients who are NAD after course 1 proceed to continuation treatment).

Oral prednisone (PDN) 40mg/m^2 in 3 divided doses for 3 days every week, from week 7-12.

Vinblastine (VBL) 6 mg/m^2 i.v. bolus, day 1 of week 7, 8, 9, 10, 11, 12 given before the MTX infusion.

Methotrexate 500 mg/m^2 24 hours-infusion with folinic acid (leucovorin) rescue, day 1 of week 7, 9, and 11. 1/10 of the dose as i.v. bolus over 30 min, followed by 9/10 of the dose as 23.5 hours infusion with 2000ml/m^2 hydration.

Folinic acid 12mg/m^2 orally is given 24 hours and 30 hours after the stop of the MTX infusion (id est: 48 and 54 hours after start of MTX therapy).

### **9.1.2.3 Continuation treatment**

Continuous oral 6-mercaptopurine (6-MP) 50mg/m^2 until the end of month 12 from therapy start.

Pulses of oral prednisone PDN 40mg/m^2 in 3 doses, day 1-5 q 3 weeks, starting at day 1 of week 7 in patients NAD after course 1 or at day 1 of week 13 in patients NAD or

AD better after course 2 until the end of month 12.

Methotrexate 20mg/m^2 orally, once weekly until the end of month 12.

Vinblastine (VBL) 6mg/m^2 i.v. bolus, day 1 q 3 weeks, starting at day 1 of week 7 in patients NAD after course 1 or at day 1 of week 13 in patients NAD or AD better after course 2 until the end of month 12.

## **9.2 GROUP 2: “LOW RISK” GROUP**

Treatment consists of an initial treatment of 6 weeks (a second course is given only to patients with persistent or progressive disease) and a continuation treatment.

The overall therapy duration is 6 or 12 months as randomly assigned.

### **9.2.1.1 Initial treatment course 1**

Continuous oral prednisone (PDN) 40mg/m^2 daily in 3 doses as a 4-week course, tapering over a period of 2 weeks.

Vinblastine (VBL) 6 mg/m^2 i.v. bolus, day 1 of week 1, 2, 3, 4, 5, 6.

### **9.2.1.2 Initial treatment course 2**

(Only in patients with intermediate or worse response after course 1)

Oral prednisone (PDN) 40mg/m^2 in 3 divided doses for 3 days every week, from week 7-12.

Vinblastine (VBL) 6 mg/m^2 i.v. bolus, day 1 of week 7, 8, 9, 10, 11, 12.

### **9.2.1.3 Continuation treatment**

The overall therapy duration is 6 months for Arm LR 6 or 12 months for Arm LR 12 .

Pulses of oral prednisone PDN 40mg/m^2 in 3 doses, day 1-5 q 3 weeks, starting at day 1 of week 7 in patients NAD after course 1 or at day 1 of week 13 in patients NAD or AD better after course 2 until the end of month 6 or 12 from therapy start.

Vinblastine (VBL) 6mg/m^2 i.v. bolus, day 1 q 3 weeks, starting at day 1 of week 7 in patients NAD after course 1 or at day 1 of week 13 in patients NAD or AD better after course 2 until the end of month 6 or 12 from therapy start.

## **9.3 GROUP 3: “MULTIFOCAL BONE DISEASE” AND “SPECIAL SITES”**

Treatment consists of an initial treatment of 6 weeks and a continuation treatment. A second course is given only to patients with progressive disease. The overall therapy duration is 6 months.

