### **9.3.2 Continuation treatment**

(starting after initial treatment at day 1 of week 7 in pts who are NAD after course 1 of initial treatment or at day 1 of week 13 in patients who are NAD or AD-better after course 2 of initial treatment)

Pulses of oral prednisone PDN 40mg/m^2 in 3 doses, day 1-5 q 3 weeks, starting at day 1 of week 7 in patients NAD after course 1 or at day 1 of week 13 in patients NAD or AD better after course 2 until the end of month 6 from therapy start.

Vinblastine (VBL) 6mg/m^2 i.v. bolus, day 1 q 3 weeks, starting at day 1 of week 7 in patients NAD after course 1 or at day 1 of week 13 in patients NAD or AD better after course 2 until the end of month 6 from therapy start.

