### 10.2 DEFINITION OF RESPONSE CRITERIA

There are three categories of response

BETTER	complete resolution	NAD
	regression	AD better
INTERMEDIATE	mixed	new lesions in one site, regression in another site
	stable	unchanged
WORSE	progression*	

\*in isolated bone disease progression is defined as appearance of new bone lesions or

lesions in other organs

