### 10.3.3 Group 3 patients with “MFB” or “SPECIAL SITES”

Brain MRI (and/or CT scans) or spinal MRI must be performed to assess the treatment response in these critical sites. In case of residual “CNS-RISK” lesions on MRI treatment must not be stopped. A biopsy of such lesions to rule out residual active disease should be considered.

Interval	Evaluation	RESPONSE	CONTINUE
week 6	after initial treatment course 1	NAD better	continuation treatment
		worse	initial treatment course 2 (risk patients arm A)
week 12	after initial treatment course 2	NAD better	continuation treatment
		worse	discuss with local coordinator
week 7 or 13-23	during continuation treatment	NAD better	continuation treatment
		worse	discuss with local coordinator

month 6	after continuation treatment	NAD better	STOP (in case of clear regression stop therapy, repeat MRI after 3 months, in case of significant residual tumor consider biopsy and discuss with local coordinator)
---------	------------------------------	------------	---

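### Group 3 treatment rules contradict each other: an intermediate response has no assigned action, and AD-better at week 6 is handled differently in 9.3.2 and 10.3.3

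*Protocol*

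**What the plan says.** Protocol 10.2 states "There are three categories of response": better, intermediate and worse. Intermediate covers unchanged disease and mixed disease, the latter being "new lesions in one site, regression in another site". A footnote to the same table says that "in isolated bone disease progression is defined as appearance of new bone lesions", or of disease in further organs.

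For Group 3, section 9.3 opens with "Treatment consists of an initial treatment of 6 weeks and a continuation treatment", adds "A second course is given only to patients with progressive disease", and sets the overall duration at 6 months. Section 9.3.2 describes continuation as "starting after initial treatment at day 1 of week 7 in pts who are NAD after course 1 of initial treatment". The only other start that it allows is week 13, for those whose status following a second course is NAD or AD better. It repeats these conditions for prednisone and for vinblastine.

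The Group 3 table in 10.3.3 has two rows (NAD/better and worse) at week 6, at week 12 and during weeks 7 or 13 to 23. At month 6 it has only NAD/better. The tables for Group 1 (10.3.1) and Group 2 (10.3.2) do give an action for an intermediate response.

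**The concern.** Group 3 is a single-arm pilot. Its aim in 6.3.1 is to lower reactivation and permanent consequences relative to historical controls from the DAL HX and LCH I and II studies. Such a comparison can be interpreted only if the reader knows what treatment the patients were meant to receive. Here one response category has no assigned action, and for another the text and the table disagree. What a patient receives after week 6 may then depend on which section the centre follows, and this happens mainly among patients without complete resolution at week 6. Allocation of treatment by response is protocol content and cannot be repaired later in an analysis plan.

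**Working it through.** The protocol gives no sample size, power or error rate for Group 3, so there is no planned figure to reproduce. The check follows each week-6 response through the three places that govern treatment.

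| Week-6 response | 9.3 | 9.3.2, read literally | 10.3.3 | Result |
|---|---|---|---|---|
| NAD | continuation | continuation from week 7 | continuation | agree |
| AD better | no course 2; continuation by default | week-7 condition not met; week-13 condition presupposes course 2 | continuation | conflict |
| Intermediate, stable | no course 2; continuation by default | neither condition met | no row | conflict and gap |
| Intermediate, mixed | depends on classification | depends on classification | no row, or course 2 if classed as worse | classification conflict |
| Worse | course 2 | week 13, if NAD or AD better after course 2 | course 2 | agree |

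**Mixed disease.** The mixed category requires a new lesion in one site with regression in another. The footnote makes a new bone lesion progression when disease is confined to bone. A multifocal-bone patient with one new and one regressing lesion meets both definitions.

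**Later time points.** After course 2, an intermediate response again has no row and does not meet the week-13 condition. At month 6, neither intermediate nor worse has a row.

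**Analogy with the other groups.** At week 6, the tables for Groups 1 and 2 both send intermediate responses to course 2. Section 9.3 excludes that in Group 3 unless disease is progressive. At week 12 the two tables part: Group 1 goes to salvage, Group 2 to continuation. Analogy therefore conflicts with 9.3 at week 6 and gives no single answer at week 12.

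**Size of the difference in planned treatment.** Assume that month 6 ends at week 26.
- Continuation from week 7, vinblastine every 3 weeks: weeks 7, 10, 13, 16, 19, 22, 25 = 7 doses.
- Course 2 (10.3.3 points to the arm A schedule, weekly in weeks 7 to 12), then continuation from week 13: 6 + 5 (weeks 13, 16, 19, 22, 25) = 11 doses.
- If continuation ended at week 23 instead, the counts would be 6 (weeks 7 to 22) and 6 + 4 = 10. The difference is 4 doses either way.

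**How many patients.** Section 2.3.1 reports that about 90% of 104 patients with multifocal bone disease regressed or resolved. The remainder is about 100% − 90% = 10%, or roughly 10 of 104. That remainder includes progressive disease, so it is a ceiling for stable plus mixed disease in that series. The series gives no split and no week-6 time point, 36 of the 104 had no systemic therapy initially, and it does not cover special sites. The week-6 share in Group 3 is unknown.

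**The case against.** The strongest reply is that 9.3 already supplies a default: initial treatment, then continuation, 6 months in all, with course 2 as the exception for progression. On that reading a stable patient simply continues. The narrow start condition in 9.3.2 looks like wording shared with Groups 1 and 2. In Group 2 (9.2.1.3) it likewise omits AD-better at week 6, although the table there sends those patients to randomised continuation. This is a fair reading of intent. It does not remove the contradiction, because 9.3.2 states a start condition, repeats it, and disagrees with both 9.3 and the table.

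A reader might infer that stable patients are barred from all treatment after week 6. The documents do not support that. It would contradict the 6-month duration in 9.3 and, for residual CNS-RISK lesions, the instruction in 10.3.3 not to stop treatment. The same literal reading would also exclude AD-better patients, whom the table sends to continuation.

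A reader might also infer that at least about 10% of patients are affected. The retrospective figure is a ceiling for that series, not a floor, and says nothing about week 6.

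Three further points on the other side stand. Section 14 makes a local coordinator available for clinical questions, which should reduce variation between centres. Section 11, and the remarks in the month-6 row, give some guidance on residual disease at the end of therapy, so the month-6 gap is the mildest. Group 3 is response-adapted by design, so differing treatment is not in itself a fault. The fault is that the adaptation rule is incomplete and inconsistent.

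**Conclusion.** The concern holds as an internal contradiction in the Group 3 rules. Stable disease at week 6 has no row in the table, and 9.3 and 9.3.2 point different ways. AD-better at week 6 is sent to continuation by 10.3.3 but does not meet the start condition in 9.3.2; this may affect more patients than the missing row. Mixed disease confined to bone can be classed in two ways.

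The planned difference between the two plausible routes is 4 vinblastine doses after week 6 (7 against 11 if therapy runs to week 26). The effect on reactivation cannot be quantified from the protocol. Section 2.3.1 associates reactivation with the type of initial treatment, but both routes use the same two drugs, and that section found no statistical impact of treatment duration.

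The consequence is limited to the non-randomised pilot, where it weakens the historical comparison in 6.3.1. No powered endpoint, error rate or randomised comparison is touched.

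**What to change.** Reconcile 9.3, 9.3.2, 10.2 and 10.3.3:
- Complete the 10.3.3 table so that every category in 10.2 has an action at week 6, at week 12, during continuation and at month 6, including worse at month 6.
- Align the start condition in 9.3.2 with 9.3 and the completed table, covering AD-better as well as intermediate responses after course 1.
- State in 10.2 which definition takes precedence when a new bone lesion appears alongside regression elsewhere in disease confined to bone.
- Record the route each Group 3 patient took after week 6, so that reactivation and permanent consequences can also be reported by treatment received.

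Which action applies to each category is a clinical decision for the study committee. The cost is protocol wording and one table, plus making sure that the existing follow-up forms capture the route. No new visits are needed.

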### **9.3.1 Initial treatment**

Continuous oral prednisone (PDN) 40mg/m^2 daily in 3 doses as a 4-week course, tapering over a period of 2 weeks.

Vinblastine (VBL) 6 mg/m^2 i.v. bolus, day 1 of week 1, 2, 3, 4, 5, 6.

### **9.3.2 Continuation treatment**

(starting after initial treatment at day 1 of week 7 in pts who are NAD after course 1 of initial treatment or at day 1 of week 13 in patients who are NAD or AD-better after course 2 of initial treatment)

Pulses of oral prednisone PDN 40mg/m^2 in 3 doses, day 1-5 q 3 weeks, starting at day 1 of week 7 in patients NAD after course 1 or at day 1 of week 13 in patients NAD or AD better after course 2 until the end of month 6 from therapy start.

Vinblastine (VBL) 6mg/m^2 i.v. bolus, day 1 q 3 weeks, starting at day 1 of week 7 in patients NAD after course 1 or at day 1 of week 13 in patients NAD or AD better after course 2 until the end of month 6 from therapy start.

## **9.4 SUPPORTIVE CARE GUIDELINES**

### Pneumocystis carinii prophylaxis

Oral sulphamethoxazole/trimethoprim, 5 mg/kg/day of the trimethoprim, divided into 2 doses/day, on 3 days per week throughout the study period and for 12 weeks thereafter (must be stopped during MTX-infusion).

Antiemetics should be given as necessary.

### Transfusions of red cells and platelets

Blood cell components should be filtered blood products and preferably irradiated (25 Gy), for prevention of GvHD.

### G-CSF

In case of prolonged neutropenia, G-CSF may be given subcutaneously or intravenously. The use of GM-CSF is not recommended.

### Intravenous immunoglobulin

may be given in cases of hypogammaglobulinemia.

## **9.5 TOXICITY**

(please fill in Toxicity sheet, Appendix)

### 6-Mercaptopurine

Myelosuppression, hepatic dysfunction (elevated transaminases and cholestatic jaundice), mucositis, dermatological manifestations, interaction with allopurinol, nausea, vomiting

### Methotrexate

Myelosuppression (leukopenia, anemia, thrombocytopenia), nausea, vomiting, mucositis (ulcerative stomatitis, diarrhea), alopecia, skin rashes, nephrotoxicity, hepatic dysfunction, liver fibrosis, encephalopathy, pneumonitis

### Prednisone

Increased appetite, centripetal obesity, fluid retention, hyperglycemia, immunosuppression, myopathy, osteoporosis, aseptic necrosis, peptic ulceration, pancreatitis, mental alteration, cataracts, hypertension, precipitation of diabetes, growth failure, amenorrhea, impaired wound healing, atrophy of subcutaneous tissue

### Vinblastine

Peripheral neuropathy: paresthesia, dysphagia, hoarseness, bone pain (esp. mandible), constipation, paralytic ileus, convulsions, myelosuppression (leukopenia, anemia, thrombocytopenia), alopecia, inappropriate ADH secretion, local pain and necrosis if

extravasated, nausea, vomiting.

### **9.5.1 Serious Adverse Events**

Any serious adverse event (death or grade III - IV non-haematological life threatening toxicity) must be reported immediately (i.e. within the next working day) by the treating institution to the the study reference center (and relayed to the local subcenters and DSMB), for further reporting according to local practice (use form in appendix).

The toxicity criteria will be the same for all participating groups (WHO-score) and appear in Appendix.

## **9.6 THERAPY MODIFICATIONS**

Try to avoid dose-reductions or delays.

### Pancytopenia

at presentation may be disease related and is then not an indication for reduction of the initial dosage.

### Infants with body weight under 10 kg:

Drug doses are calculated based on body surface area (BSA) only and dose is adjusted for age as follows:

< 6 months	50% of dose calculated form BSA
> 6 months < 12 months	75% of dose calculated from BSA
> 12 months	100% of dose calculated from BSA

### Bone marrow toxicity:

In case of good response to therapy it is recommended to wait for hemapoetic recovery. An absolute neutrophil count greater than  $1.0 \times 10^9/l$  and a platelet count greater than  $100 \times 10^9/l$  are essential before starting each course of therapy except for the first dose. In case of persistent disease activity it is recommended to continue protocol regardless of the hematologic values.

### Hepatotoxicity:

Samples for determination of liver enzymes (ALT/GOT, AST/GPT) must be

drawn immediately prior to a course of i.v. MTX. If values are 10-20N (i.e. 10-20 times higher than normal values) wait 48 hrs and recheck to ensure that the levels are decreasing. Discontinue TMP/SMZ if the transaminase elevation persists or increases, and withhold chemotherapy until the value is <10N, then resume full dose chemotherapy. Resumption of TMP/SMZ prophylaxis is left to the investigator's discretion. Should therapy be withheld for elevated transaminases during initial therapy, resume therapy at point of interruption. Transaminase values of 20N mandate holding therapy until the level returns to <10N. Persistence of values >20N for >2 weeks requires an evaluation including: bilirubin, alkaline phosphatase, coagulation tests, albumin, total protein and hepatitis serologies. A liver biopsy should be considered before additional therapy is given to help to distinguish hepatic toxicity from LCH involvement or sclerosing cholangitis. Under such circumstances, please contact the local coordinator.

#### Nephrotoxicity

For patients with a GFR by creatinine clearance of less than 60 ml/min/1.73m^2 delay MTX and repeat clearance after hydration.

#### Gastrointestinal toxicity

In case of severe mucositis or diarrhea, therapy should be discontinued until recovery and then reinstated without dose reduction. To prevent constipation in patients treated with vinblastine regular administration of mild laxatives is recommended. Serious constipation with paralytic ileus requires cessation of vinblastine administration.

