#### Neurotoxicity

In the event of significant toxicity (extensive weakness, severe paresthesia, severe ileus), VBL may be temporarily discontinued and resumed at 50% dose when toxicity resolves. Contact the local study coordinator before discontinuing VBL. Increase to maximum tolerated dose (not exceed protocol dose) as soon as possible.

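### Section 9.6 gives two different rules for vinblastine in ileus: a mandatory stop under Gastrointestinal toxicity, and an optional stop after coordinator contact under Neurotoxicity

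*Protocol*

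**What the plan says.** Two consecutive paragraphs of Protocol section 9.6 (Therapy modifications) deal with ileus.

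- **Gastrointestinal toxicity:** "Serious constipation with paralytic ileus requires cessation of vinblastine administration". No coordinator step, duration or restart dose is given for ileus. For severe mucositis or diarrhoea, the same paragraph does provide a restart: "therapy should be discontinued until recovery and then reinstated without dose reduction".
- **Neurotoxicity:** the examples of significant toxicity are weakness, paresthesia and, third, ileus: "severe ileus), VBL may be temporarily discontinued and resumed at 50% dose when toxicity resolves". Two instructions follow: "Contact the local study coordinator before discontinuing VBL" and "Increase to maximum tolerated dose (not exceed protocol dose) as soon as possible".

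Section 9.5 includes paralytic ileus in its list of vinblastine toxicities, in a run of items that opens with peripheral neuropathy. Section 9.6 itself opens with general advice against reducing or delaying doses. Vinblastine is part of treatment in all three groups (sections 9.1 to 9.3).

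**The concern.** A dose-modification rule should tell the treating physician what to do when the event occurs. Here the same drug and the same complication have one rule that compels a stop and another that permits it. A physician who regards vinblastine ileus as autonomic neuropathy would look under Neurotoxicity, and the list in section 9.5 encourages that view. There the physician finds no obligation to stop, against a general preference for keeping doses on time. At stake is a further vinblastine dose for a child in whom the neighbouring paragraph forbids it. The restart is a second, smaller uncertainty: a reader of the gastrointestinal paragraph alone cannot tell whether the stop is temporary or permanent.

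**Working it through.** There is no figure to reproduce. The check sets the two rules side by side and tests what a site may do under each.

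**Do the triggers overlap?** One paragraph speaks of paralytic ileus with serious constipation, the other of severe ileus. Neither attaches a toxicity grade, and section 9.6 gives no definition or precedence rule to tell them apart. A child with severe paralytic ileus and constipation meets both descriptions. This does not depend on how the list in section 9.5 is read, because the Neurotoxicity paragraph names ileus itself.

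**What may a site do when the next vinblastine dose is due?**

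| Action | Gastrointestinal toxicity | Neurotoxicity |
|---|---|---|
| Give the dose | Forbidden | Allowed, since the stop is optional |
| Call the coordinator, then withhold | Allowed | Allowed |
| Withhold first, call afterwards | Allowed | Contrary to the order stated |
| Resume at 50% after resolution, then increase | Not addressed | Prescribed |
| Never resume | One possible reading | Not foreseen |

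The first row is the conflict: one paragraph allows what the other prohibits. The second row shows that one course of action satisfies both. The last two rows show that restart is unsettled rather than plainly contradictory. The gastrointestinal paragraph is silent on restart after ileus, and only the other paragraph supplies a rule.

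**How much delay could the call cause?** Vinblastine is an intravenous bolus on day 1 of each week during the initial courses and every 3 weeks during continuation. To stop it is to omit the next bolus, so the time available for the call is at most 1 × 7 = 7 days in initial treatment and 3 × 7 = 21 days in continuation. Contact first delays the stop only if a dose falls due before the coordinator is reached.

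**How often?** The protocol gives no ileus rate, and its account of toxicity in the earlier studies (section 2) does not mention ileus. The number affected cannot be computed.

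**The case against.** The strongest reply is that both paragraphs can be obeyed: call, then withhold. They stand next to each other, and a careful reader would let the specific mandatory sentence override the broader optional one. Section 14 makes the local coordinator available for clinical questions. Section 2 reports that no patient in the first international study, which had a vinblastine arm, was withdrawn for toxicity, although withdrawal is not the same as a held dose. This reply limits the practical risk. It does not remove the inconsistency, because nothing in section 9.6 says which sentence prevails and the optional one still permits the dose.

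A reader might infer more than the text supports in three ways.

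- **That calling first leaves a child exposed while the site waits.** With doses 7 or 21 days apart, this would seldom happen.
- **That prior contact is itself an error because other paragraphs of section 9.6 do not ask for it.** Under Hepatotoxicity, for instance, the hold comes first ("Transaminase values of 20N mandate holding therapy until the level returns to <10N"), and "Under such circumstances, please contact the local coordinator" follows only in the context of values persistently above 20N for more than 2 weeks. Those rules concern other toxicities and largely other drugs. A contact step specific to vinblastine neurotoxicity is a legitimate choice, and the comparison shows no mistake.
- **That the 50% restart clearly governs after paralytic ileus.** The gastrointestinal paragraph provides reinstatement for mucositis and diarrhoea but only cessation for ileus. That contrast leaves a permanent stop open as a reading.

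**Conclusion.** The point stands as a minor correction of safety wording. Section 9.6 requires vinblastine to be stopped in one paragraph and makes the stop optional, after prior contact, in the next, for triggers that overlap and are not graded. The realistic harm is continued dosing by a site that follows the optional wording.

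The conclusion rests on the plain text of the two paragraphs and on the clinical overlap between severe and paralytic ileus. Frequency is unknown and assumed low.

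A reader might also expect consequences for the statistics, for example through the per-protocol set in section 16.3, which excludes unjustified dose modification. The document does not support that: a stop for ileus is licensed by one paragraph or the other and would not naturally count as unjustified. No between-arm bias and no effect on the sample size or the intention-to-treat analyses is claimed.

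**What to change.** 1. Delete severe ileus from the examples in the optional sentence under Neurotoxicity. The optional stop with prior contact can remain for weakness and paresthesia.
2. State one rule in section 9.6 and cross-reference it from the other paragraph, for example: *In paralytic or severe ileus the next vinblastine dose must be withheld. Inform the local coordinator; the stop does not depend on that contact.*
3. Ask the sponsor to state whether vinblastine may be restarted after paralytic ileus. If so, the rule should say whether the existing schedule applies (50% dose after resolution, then increase up to the protocol dose). If the stop is meant to be permanent, it should say that. This is a clinical decision that the present text does not settle.

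The cost is a few sentences and a cross-reference in an amendment, with no change to the sample size, visits or analyses.
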